COVID-19	COronaVIrus Disease 2019
CSP	Clinical Study Protocol
ECG	ElectroCardioGram
eCRF	electronic Case Report Form
eGFR	estimated Glomerular Filtration Rate
EOT	End Of Treatment
FAS	Full Analysis Set
IP	Investigational Product
LOCF	Last Observation Carried Forward
K+	Potassium
MedDRA	Medical Dictionary for Regulatory Activities
РОСТ	Point-of-Care Test
PPS	Per Protocol Set
QD	once daily
QTcF	QT interval corrected by the Fridericia method
RAASi	Renin-Angiotensin-Aldosterone System Inhibitor
SAE	Serious Adverse Event
SAP	Statistical Analysis Plan
sK+	serum potassium
SoA	Schedule of Activities
SSO	Safety Set Open
SSR	Safety Set Randomized
SZC	Sodium Zirconium Cyclosilicate
TCO2	Total carbon dioxide
TID	Three times daily
UACR	urine albumin-to-creatinine ratio

AMENDMENT HISTORY

Category*: Change refers to	Date	Description of change	In line with the CSP?	Rationale
Other	01-Dec-2022	Amended subgroup and sensitivity analyses to be conducted. Amended covariates to be included in sensitivity analysis of primary endpoint.	No	Due to the early termination of study some planned analyses cannot be performed due to small sample size. Updating SAP to clarify which subgroup and sensitivity analyses are no longer being performed.
Multiple Testing Procedure	01-Dec-2022	Clarified data presentation of multiplicity process due to early termination of the study	No	Clarifying how p-values will be displayed in data presentations due to early termination of study.
Other	30-May-2022	Updated language to reflect changes in protocol v6.0. Added details regarding interim analysis.	Yes, v6.0	Protocol update includes interim analysis to be described in the SAP.
Primary or secondary endpoints	09-Aug-2021	Changed i-STAT to Point of Care Test (POCT) throughout SAP in line with CSP	Yes, v4.0	Protocol updated to expand POCT options in addition to i-STAT.
Statistical analysis method for the primary of secondary endpoints	09-Aug-2021	Added POCT type to multivariable analyses of primary and secondary endpoints	Yes, v4.0	Considered important to control for confounding difference from POCT type used by site.
CCI				

				gap results but providing variables needed to enable calculation.
Addition of analysis visit windows	09-Aug-2021	Added analysis visit windows	No	This change expands visit windows to allow additional assessments to be included in summaries by visit.

* Pre-specified categories are

Primary or secondary endpoints; Statistical analysis method for the primary or secondary endpoints; Derivation of primary or secondary endpoints; Multiple Testing Procedure; Data presentations; Other

1 STUDY DETAILS

1.1 Study objectives

Objectives	Endpoints
Primary	
• To evaluate the efficacy of sodium zirconium cyclosilicate (SZC) as compared to placebo in maintaining normal serum potassium (sK+) in patients with hyperkalemia and metabolic acidosis associated with chronic kidney disease (CKD)	• Occurrence (yes/no) of patients having normal sK+ between 3.5 and 5.0 mmol/L inclusive at end of treatment (EOT), Day 29, without need for rescue treatment for hyperkalemia at any point during the randomized phase
Secondary	
• To evaluate the efficacy of SZC as compared to placebo in increasing serum bicarbonate in patients with hyperkalemia and metabolic acidosis associated with CKD	 Mean change in serum bicarbonate at Day 29 compared to baseline (Day 1) Occurrence (yes/no) of patients having an increase in serum bicarbonate of ≥2 mmol/L from baseline (Day 1) to EOT (Day 29) without need for rescue treatment for metabolic acidosis (low bicarbonate) Occurrence (yes/no) of patients having an increase in serum bicarbonate of ≥3 mmol/L from baseline (Day 1) to EOT (Day 29) without need for rescue treatment for metabolic acidosis (low bicarbonate) Occurrence (yes/no) of patients having an increase in serum bicarbonate of ≥3 mmol/L from baseline (Day 1) to EOT (Day 29) without need for rescue treatment for metabolic acidosis (low bicarbonate) Occurrence (yes/no) of patients having bicarbonate ≥22 mmol/L at EOT (Day 29) without need for rescue treatment for metabolic acidosis (low bicarbonate)
	•
• To evaluate the efficacy of SZC as compared to placebo in normalizing sK+ and increasing serum bicarbonate in patients with hyperkalemia and metabolic acidosis associated with CKD	 Occurrence (yes/no) of patients having normal sK+ between 3.5 and 5.0 mmol/L inclusive at EOT (Day 29) and an increase in serum bicarbonate of ≥3 mmol/L from baseline (Day 1) to EOT (Day 29) without need for rescue treatment for hyperkalemia or metabolic acidosis (low bicarbonate).
	 Occurrence (yes/no) of patients having normal sK+ between 3.5 and 5.0 mmol/L inclusive and bicarbonate ≥22 mmol/L at EOT (Day 29) without need for rescue treatment for hyperkalemia or metabolic acidosis (low bicarbonate).
• To describe the need for rescue treatment with sodium bicarbonate for metabolic acidosis (low bicarbonate) in SZC and placebo arms	• Occurrence (yes/no) of patients needing rescue treatment for serum bicarbonate (≤15 mmol/L) any time during the randomized phase
Safety	
• To evaluate the safety and tolerability of SZC as compared to placebo in patients with	• Safety and tolerability will be evaluated in terms of Adverse Events (AEs), vital signs, clinical laboratory

hyperkalemia and metabolic acidosis associated with CKD assessments, and Electrocardiogram (ECG). Assessments related to AEs cover: • Occurrence/frequency • Relationship to SZC/placebo as assessed by investigator • Intensity • Seriousness • Death • AEs leading to discontinuation of SZC/placebo	hyperkalemia and metabolic acidosis associated with CKD	assessments, and Electrocardiogram (ECG). Assessments related to AEs cover: • Occurrence/frequency
with CKD Assessments related to AEs cover: • Occurrence/frequency • Relationship to SZC/placebo as assessed by investigator • Intensity • Seriousness • Death • AEs leading to discontinuation of SZC/placebo	with CKD	Assessments related to AEs cover: • Occurrence/frequency
 Occurrence/frequency Relationship to SZC/placebo as assessed by investigator Intensity Seriousness Death AEs leading to discontinuation of SZC/placebo 		Occurrence/frequency
 Relationship to SZC/placebo as assessed by investigator Intensity Seriousness Death AEs leading to discontinuation of SZC/placebo 		
 Intensity Seriousness Death AEs leading to discontinuation of SZC/placebo 		 Relationship to SZC/placebo as assessed by investigator
 Seriousness Death AEs leading to discontinuation of SZC/placebo 		• Intensity
 Death AEs leading to discontinuation of SZC/placebo 		Seriousness
AEs leading to discontinuation of SZC/placebo		• Death
		 AEs leading to discontinuation of SZC/placebo

1.2 Study design

This is a prospective, randomized, double-blind, placebo-controlled, parallel, multicenter, Phase IIIb study to investigate the safety and efficacy of SZC in patients with hyperkalemia and low bicarbonate (or metabolic acidosis).

The study will be conducted in the United States (US) at approximately 35 investigative sites.

This study consists of a short screening visit (Day 1), an open-label correction period (up to 48 hours), a 4-week randomized treatment period, and a follow-up period (7 days after the last administration of study medication). The total study treatment duration, consisting of open-label and randomized periods, will be 29 days.

Screening will be performed using potassium and bicarbonate value from a study-approved point-of-care test (POCT) to determine eligibility of consenting patients to enter the openlabel correction phase. Patients who meet the POCT eligibility criteria of serum potassium (sK+) between 5.1-5.9 mmol/L inclusive, AND serum bicarbonate between 16-20 mmol/L inclusive, will be enrolled into the open-label correction phase. All baseline parameters should be measured/collected prior to administration of the first dose of study drug in the open-label initial phase.

In the open-label initial phase, patients will receive open-label SZC orally at a dose of 10 g three times daily (TID) for up to 48 hours, depending on POCT potassium value.

Patients who achieve normokalemia (K+ between 3.5 and 5.0 mmol/L inclusive) within 24-48 hours will be randomized 1:1 into the double-blind randomized treatment phase to receive 10 g SZC or placebo once daily (QD) starting dose for the following 28 days. Patients who achieve normokalemia after 24 hours will be randomized and will not need to continue on 10 g SZC TID for another 24 hours.

Study treatment will end with the Day 29 visit, which will be followed by the end of study visit 7 days after the last administration of study medication.

1.2.1 Randomization

Subjects who are normokalaemic (NK; $3.5 \le sK + \le 5.0 \text{ mmol/L}$) within 24 to 48 hours of enrolment in the open-label correction phase will be randomized 1:1 to either SZC 10g QD or placebo 10g QD. Randomization will be performed using randomly permuted blocks. The randomization codes will be computer generated and loaded into the IxRS database.

1.3 Number of subjects

- Prior data: Proportion of patients with serum bicarbonate between 16-20 mmol/L inclusive who had a 3 mmol/L or greater increase in serum bicarbonate with SZC versus placebo from ZS-004,²⁰ Global Harmonize trial,²¹ and ZS-005.²²
- SZC: 92/235 = 0.39 achieved an increase in serum bicarbonate $\ge 3 \text{ mmol/L}$
- Placebo: 7/40 = 0.175 achieved an increase in serum bicarbonate $\ge 3 \text{ mmol/L}$
- Sample size estimate*
 - \circ 20% absolute difference:
 - Alpha=0.05, Power=80%
 - Control=0.175 with serum bicarbonate increase of 3mmol/L or more
 - SZC=0.39 with serum bicarbonate increase of 3mmol/L or more
 - *Actual effect size = 0.215
 - \circ N=68 per group (136)
 - N=148 (accounting for 8% drop-out from initial phase to randomized placebocontrolled phase)

*Sample size would be smaller if based on primary endpoint of mean sK+ (N=18 per arm).

Approximately 477 patients will be screened. Approximately 148 patients will be enrolled to the open-label phase of the study to achieve 136 randomly assigned to study intervention.

2 ANALYSIS SETS

2.1 Definition of analysis sets

Screened Set

All subjects who were screened for inclusion in the open-label run-in period of the study. This analysis set will be used to describe the demographics of subjects considered for inclusion in the study. The assignment of subjects to a treatment group for analysis is not applicable.

Safety Set Open

All patients enrolled in the open-label correction phase who took at least 1 dose of study drug. The Safety Set Open (SSO) analysis set will be used to describe the safety characteristics of SZC during the open-label period. Patients will be analyzed as a single group.

Safety Set Randomized

All patients who achieve normokalemia at the end of the open-label correction phase and who received at least one dose of either SZC or placebo during the randomized placebo-controlled phase. The Safety Set Randomized (SSR) analysis set will be used to describe the safety characteristics of SZC or placebo during the randomized placebo-controlled phase. Patients will be analyzed according to the investigational product (IP) received during the randomized placebo-controlled phase.

Full Analysis Set

All patients who achieve normokalemia (K+ between 3.5 and 5.0 mmol/L inclusive) at the end of the open-label correction phase and enter the randomized placebo-controlled phase. The Full Analysis Set (FAS) will be the primary analysis set used for the primary, secondary and CCL Patients will be analyzed on an intent-to-treat basis according to their randomized IP.

Per Protocol Set

The Per Protocol Set (PPS) is defined as all patients in the FAS without any important protocol deviations leading to exclusion from the PPS. Patients will be analysed according to their randomized IP. The PPS will be used for sensitivity analysis of the primary and secondary endpoints.

Protocol deviations are defined as any change, divergence, or departure from the study design of procedures defined in the clinical study protocol (CSP). Important protocol deviations are a subset of protocol deviations and may significantly impact the correctness, accuracy, and/or reliability of the study data or that may significantly affect a subject's rights, safety, or wellbeing. Important protocol deviations which should lead to exclusion from the PPS will be defined by the Sponsor before database lock by judging the importance of the deviations upon the primary efficacy endpoint.

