2.2 Violations and deviations

Subjects will be assessed by comparison of their electronic case report form (eCRF) data with the criteria below; protocol waivers will not be taken into consideration (e.g. if a subject younger than 18 enters the study on a protocol waiver, the subject would still be excluded from the PPS).

The following criteria may be considered as important protocol deviations which have a major effect on efficacy or that could potentially affect the interpretability of the study results and which should lead to exclusion from the PPS.

- Subjects who failed any of the inclusion or exclusion criteria of the study.
- Inappropriate compliance with study treatment during the randomized placebocontrolled phase of the study, e.g. treatment compliance of less than 80% or greater than 120%
- All prohibited medications which are administered during the randomized placebocontrolled phase of the study. Prohibited medications include patients starting on renin-angiotensin-aldosterone system inhibitor (RAASi) therapy during the trial Note: RAASi therapies: Angiotensin-converting enzyme inhibitor (ACEi), angiotensin II receptor blocker (ARB) or angiotensin receptor-neprilysin inhibitor (ARNi) are permitted to be continued at the same dose as baseline.
- Errors in treatment allocation. Any subject who received incorrect study treatment compared with randomized study treatment at any time during the study
- Any subject unblinded during the study
- Rules for rescue medication for hyperkalemia or metabolic acidosis violated
- Start of double-blind study medication prior to randomization date
- Subject with first dose prior to baseline evaluations.

In addition, protocol deviations will be defined by the Sponsor before database lock as coronavirus disease 2019 (COVID-19) pandemic related or not by judging the root cause of the protocol deviation, in line with FDA guidance (FDA Guidance on Conduct of Clinical Trials of Medical Products during COVID-19 Public Health Emergency; March 2020). The following criteria may be considered as indicative of a protocol deviation related to the COVID-19 pandemic.

- Missed in-person visit due to COVID-19 illness and/or COVID-19 public health control measures
- Study visit out of window due to COVID-19 illness and/or COVID-19 public health control measures
- Missed doses due to COVID-19 illness and/or COVID-19 public health control measures

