3.3 Efficacy Variables

3.3.1 Potassium

Whole blood samples will be analyzed locally using POCT devices to generate K+ for the purposes of study inclusion, dose adjustments, and monitoring. Samples drawn at the same timepoints will be prepared and shipped to the central laboratory for analysis of sK+. In the event that hemolysis or other artifacts are suspected based on the reported POCT K+ result, the blood samples must be re-drawn to confirm the result and only the confirmatory sample result will be reported.

The primary endpoint will use the central laboratory sK+ measurement from Visit 7 if available and no use of rescue medication for hyperkalaemia has occurred. Missing measurements at Visit 7 will be imputed as follows:

(i) If Visit 7 central laboratory sK+ is missing

Visit 6 (or an unscheduled assessment which occurs between visits 6 and 7) central laboratory sK+ will be used in its place under the principle of last observation carried forward (LOCF). If multiple measurements are available, the closest measurement to the scheduled date of Visit 7 will be used.

(ii) If central laboratory sK+ is missing for Visits 6 and 7

sK+ will be replaced by POCT values adjusted to reflect the mean difference between POCT and sK+ values from all available (including screening, baseline and unscheduled visits) paired laboratory samples in both treatment groups. The mean difference will be estimated using a summary statistic of the difference in all pairs and will not adjust for baseline characteristics. If a Visit 7 POCT value is available the adjusted value for this will be used unless missing, in which case the adjusted Visit 6 POCT will be used. If an unscheduled POCT assessment which occurs between visits 6 and 7 is available, then the closest POCT assessment to the scheduled date of visit 7 will be used.

(iii) No sK+ or POCT K available for Visits 6 or 7

The subject will be classified as non-evaluable for primary and secondary efficacy endpoints which include sK+ measurements in their definition.

Normokalaemia is defined as $3.5 \le sK+ \le 5.0$ and hyperkalaemia is defined as sK+ > 5.0 where the sK+ value used will be the result of the imputation approach described above.

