4.2.7.3 Secondary Efficacy Analyses

1 Mean change in serum bicarbonate from baseline (Day 1) to Day 29 (Visit 7) in SZC versus placebo arm.

Serum bicarbonate will be summarized and listed in the FAS using the visits of Baseline (Visit 1), randomization (Visit 3) and Day 29 (Visit 7). Patients with missing serum bicarbonate values at visit 7 will have these imputed with serum bicarbonate values from visit 6 if available, as described in section 3.3.2. The mean change in serum bicarbonate from baseline (Day 1) will be analyzed using analysis of covariance (ANCOVA) analyses at the significance level 5% (2-sided), with randomized treatment as main effect and baseline bicarbonate as covariate. For patients needing rescue treatment for low bicarbonate, the last value of the POCT bicarbonate during the randomized period prior to rescue treatment will be analyzed. The analysis will be based on the FAS.

Documentation will be provided on the underlying assumptions for the ANCOVA model. This will include a check that the residuals are approximately normally distributed by plotting a histogram of the residuals for the model as well as a Shapiro-Wilk test which will reject the null hypothesis that the residuals are normally distributed if p<0.05. Secondly, the homogeneity of variance will be visually checked through an inspection of a plot of residuals versus predicted values from the model. Finally, the homogeneity of slopes will be determined by conducting an ANCOVA analysis where the dependent variable is Day 29 (Visit 7) serum bicarbonate and the independent variables are randomized treatment group, baseline serum bicarbonate. If p>0.05 for the interaction term, then we will accept the homogeneity of the treatment slopes.

Estimand Attributes

Endpoint:

• Change in serum bicarbonate at Day 29 (Visit 7) from baseline

Population:

• All subjects who achieve normokalemia at the end of the open-label correction phase, meet inclusion/exclusion criteria and are randomized

Treatment:

• SZC or Placebo. Patients with $sK+ \ge 6.0 \text{ mmol/L}$ will be managed with rescue therapy employing local standard of care.

- Discontinuation of treatment (Treatment policy strategy, i.e. regardless of the intercurrent event)
- Use of rescue therapy for hyperkalaemia at any point during the placebo-controlled period (Treatment policy strategy, i.e. regardless of the intercurrent event).

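### The Full Analysis Set and the Safety Set Randomized both require achieved normokalemia, so a patient randomized in error without it leaves the intent-to-treat set and, if dosed, every randomized-phase safety table

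*SAP*

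**What the plan says.** SAP section 2.1 defines the FAS as "All patients who achieve normokalemia (K+ between 3.5 and 5.0 mmol/L inclusive) at the end of the open-label correction phase", with entry into the randomized phase as a second condition. It adds: "Patients will be analyzed on an intent-to-treat basis according to their randomized IP". The SSR is defined as "All patients who achieve normokalemia at the end of the open-label correction phase and who received at least one dose of either SZC or placebo" in the randomized phase, analysed by product received.

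Section 1.2.1 makes normokalemia within 24 to 48 hours the condition for being randomized. Section 2.2 deals with patients who should not have been in the study through the PPS; its first exclusion criterion reads "Subjects who failed any of the inclusion or exclusion criteria of the study". Allocation errors and waivers are handled there as well.

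The general rules in section 4 base safety and exposure summaries on the Safety Set Open (SSO) and the SSR, and restrict SSO analyses to Visits 1 and 2.

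The population line of the primary estimand (section 4.2.7.1) asks for normokalemia and randomization. For secondary endpoints #1 to #7 (section 4.2.7.3) it reads "All subjects who achieve normokalemia at the end of the open-label correction phase, meet inclusion/exclusion criteria and are randomized".

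**The concern.** If every randomized patient is normokalemic, the normokalemia clause in the two definitions does nothing. It takes effect only when someone is randomized without meeting the criterion, and then it removes that patient. An intent-to-treat set should not lose a randomized patient because an entry condition turns out not to have been met. A safety set for the randomized phase should not lose someone who took randomized treatment.

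The safety side is the stronger half. A patient randomized just outside the range, say at 3.4 or 5.1 mmol/L, starts the blinded phase at the edge of the potassium range, and section 3.4.2 singles out potassium below 3.5 mmol/L for separate reporting. That patient's events would not be counted in either arm.

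There is also an internal inconsistency. Other eligibility failures stay in the FAS and leave only the PPS, whereas this one leaves the FAS and, because the PPS is a subset of the FAS, the PPS too.

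**Working it through.** The point turns on set membership, so the check is to follow one patient through the SAP: randomized, dosed, and not normokalemic at the end of the open-label phase.

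**Efficacy sets**
- FAS (2.1): needs normokalemia and entry into the randomized phase. The first fails, so the patient is out.
- PPS (2.1): a subset of the FAS, so out.
- Important-deviation summary (4.2.2): produced for the FAS, so this patient's own deviation is not counted in it.

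**Randomized-phase safety**
- SSR (2.1): needs normokalemia and one randomized-phase dose. The first fails, so the patient is out.
- Adverse events (4.2.8.1): randomized-period events are tabulated on the SSR; the SSO tables take open-label events only.
- Laboratory data, vital signs and ECG (4.2.8.3 to 4.2.8.5): SSO tables stop at the open-label visits; later visits are on the SSR.
- Weight and BMI, and exposure (4.2.8.6, 4.2.8.7): by treatment on the SSR only.
- Deaths (4.2.8.2): no set is named, so the section 4 rule (SSO and SSR) applies.

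**Where the patient still appears**
- Adverse event listings for all subjects (4.2.8.1) and the listing of all deaths (4.2.8.2).
- Disposition on the screened set, including the randomized and the randomized-and-treated counts, and the table of reasons for exclusion from each set (4.2.1).
- The SSO tables for the open-label period.

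The disposition count of patients randomized and treated could therefore exceed the SSR denominator.

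**Estimand lines against the FAS**
- Primary: normokalemic and randomized, which matches the FAS as now written.
- Secondary #1 to #7: the same plus an eligibility condition that the FAS lacks. Section 4.2.7.3 nevertheless runs these analyses in the FAS, so the stated population and the analysis set disagree.

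**Is this a power problem?** First the SAP's own figure (section 1.3): control 0.175, SZC 0.39, two-sided alpha 0.05, power 80%.

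n per arm = [z(0.975)·√(2·p̄·(1−p̄)) + z(0.80)·√(p₁(1−p₁) + p₂(1−p₂))]² / (p₂−p₁)², with p̄ = 0.2825

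= (1.2479 + 0.5204)² / 0.215² = 67.6, hence 68 per arm and 136 in total. Then 136/0.92 = 147.8, hence 148. Both figures reproduce.

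The number randomized in error is not stated. Taking an assumed range, split evenly between arms:

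| Excluded of 136 | Share | Power on the sizing endpoint |
|---|---|---|
| 0 | 0.0% | 0.802 |
| 2 | 1.5% | 0.796 |
| 5 | 3.7% | 0.787 |
| 7 | 5.1% | 0.781 |
| 14 | 10.3% | 0.757 |

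A few exclusions barely move power. The defect lies in the definitions, not in the sample size.

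**The case against.** By design only normokalemic patients are randomized, so the FAS and the randomized set coincide unless someone makes an error. The criterion precedes randomization and is the same for both arms, so dropping those who missed it should not favour either. The FAS as written also matches the primary estimand's population, and the patient does not vanish from the report. All of this stands, and it limits the size of the point. It does not justify the clause, which has no effect except to remove a randomized patient. Nor do listings replace counts by arm.

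A reader might infer something larger: that correctly randomized patients would also be lost, because point-of-care potassium guides the open-label phase while section 3.3.1 defines normokalaemia on a value described as "where the sK+ value used will be the result of the imputation approach described above". The documents do not support this. That imputation concerns missing Visit 7 values and serves the endpoint; it cannot be applied at randomization. Sections 1.2, 1.2.1 and 2.1 each carry their own 3.5 to 5.0 mmol/L criterion, and section 3.3.1 assigns the point-of-care value to inclusion and monitoring. Any percentage for such losses would need an assumed potassium distribution and assumed assay agreement, none of which the SAP gives. With an assumed SD of 0.35 the share runs from 0.7% (mean 4.5, bias −0.1, difference SD 0.10) to 20.0% (mean 4.7, bias +0.1, difference SD 0.30), so it carries no information. What stands is only that section 2.1 does not name the assay.

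A reader might also take the eligibility phrase in the secondary estimands to remove patients. It does not, since section 4.2.7.3 fixes the FAS as the analysis set. It is a mismatch of wording.

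**Conclusion.** The point holds for patients randomized without normokalemia, and only for them. Such a patient is excluded from a set described as intent-to-treat and, if dosed, from all SSR-based randomized-phase safety tables. This follows from the wording of section 2.1 and the safety rules in sections 4 and 4.2.8; no other provision brings the patient back into a randomized-phase table. The number affected is not given and may be zero. Neither a bias between arms nor a material loss of power is shown. It should be corrected because it concerns intent-to-treat integrity and the completeness of safety reporting, and the correction is cheap.

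**What to change.** 1. Section 2.1, FAS: all randomized patients, analysed as randomized.
2. Section 2.1, SSR: all randomized patients who took at least one randomized-phase dose, analysed by treatment received.
3. Section 2.2: add randomization without meeting the normokalemia criterion to the deviations leading to PPS exclusion, naming the potassium measurement against which it is judged.
4. Sections 4.2.7.1 and 4.2.7.3: align the population line of the primary and secondary estimands with the revised FAS, and delete the eligibility condition from secondary #1 to #7.

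The cost is SAP wording. The small downside is that a few patients who did not meet the randomization criterion stay in the FAS. For the primary endpoint the PPS sensitivity analysis (section 4.2.7.2) would show the result without them, once item 3 is in place. For the secondary endpoints there is no such check, because their sensitivity analyses are cancelled (sections 4.2.7.4 and 6).
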